#### Simulated study pairwise power with N=100 randomized individuals per arm

Increased # of Non-Use Days With Treatment	Use 0%	Underreporting 20%	Percentage 40%
2.27	.635	.570	.515
3.16	.886	.873	.777
3.94	.974	.968	.915

Under these assumptions, an improvement of 3.16 days in the 30 day evaluation period can be reliably detected with >85% power if the underreporting percentage is bounded by 20%. When delta approaches 4, in excess of 90% power is available. Note that the standard errors for the first column results are .015, .010 and .005.

The above excludes the 5% of the randomized individuals who fail to enter the evaluation period. If one were to impute the maximally pessimistic situation (all treated use daily, all control use never) for these cases then simulated power is 77% for the difference of 3.94 days, no underreporting.

#### **10.2.1** Projected Number of Sites

It is anticipated that 10-12 sites will participate in the trial.

#### **10.2.2** Projected Number of Participants per Site

It is anticipated that at least 10 sites will target accrual of 30 randomized cases per site, at least 1.5 per month over a 20-month recruitment period.

#### **10.3** Statistical Methods for Primary and Secondary Outcomes

The primary endpoint will be analyzed with the 2 sample Wilcoxon statistic.

The rich data set will permit a series of additional analyses addressing secondary objectives 1-10. Safety analyses are outlined in Section 10.9. The Treatment Effectiveness Score (TES) (Ling et al. 1997) is the percentage of the scheduled urine drug screens that were both provided and negative. TES will be evaluated during the evaluation period for both cocaine and opioid use. Simple contrasts of the treatment arms will be performed with the Wilcoxon statistic. Additional analyses will examine the primary endpoint adjusting for strata and other covariate effects including gender, age and race. Repeated-measurement analysis models will be used to explore presence of time-related treatment effects, including severity of cravings and level of mood disturbance. Additional analyses will include assessment of treatment effect in the preevaluation period (Days 1-24), over the course of the entire treatment period and during the follow-up period. Changes occurring over the treatment period in severity and type of drugrelated problems and in quality of life will be summarized and compared between treatment groups using the two sample Wilcoxon test for continuous outcomes or the chi-square test or Fisher's Exact Test for categorical outcomes.

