#### 5.5 Number of CTP Sites

The multi-site trial will involve 10-12 community treatment programs across the CTN.

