#### 7.2 Randomization

Immediately following successful induction onto XR-NTX and a final assessment of eligibility, participants will be randomly assigned to one of the three conditions: (BUP4+XR-NTX), (BUP16+XR-NTX) or (PLB+XR-NTX) for 8 weeks of treatment. Random assignment will be on a 1:1:1 ratio to one of three conditions. Randomization will be stratified according to site and opioid use levels according to the following strata:

- High, defined as 1) ever injected an opioid; 2) greater than or equal to 2 years of regular opioid use (per ASI); or 3) opioid use on 20 or more days in the month preceding screening (per TLFB)
- Low, defined as not meeting criteria for high opioid use

The randomization procedure will be conducted in a centralized process through the CTN Data and Statistics Center (DSC), and randomization assignments will not be conveyed to staff or participants. The DSC statistician will generate the randomization schedule using balanced blocks of varying sizes within strata to ensure lack of predictability along with relative equality of assignment across treatment groups. The DSC statistician will review randomization data on a regular basis to ensure that the scheme is being implemented according to plan. A randomization slot, once used, will not be re-allocated.

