#### **10.2** Rationale for Sample Size and Statistical Power

The study has been designed to include 300 individuals randomly assigned at a 1:1:1 ratio to the 3 treatment arms. The sample size was developed from a simulation study of the anticipated trial characteristics considering the number of abuse days, withdrawal probabilities, probability of underreporting abuse and effect size. Prior studies of a similar population (NIDA CTN-0007 Motivational Incentives for Enhanced Drug Abuse Recovery: Methadone Clinics) indicates that in a thirty day period, participants had about 9 cocaine abuse days, with a standard deviation nearly the size of the mean (mean=9.5, sd=8.5). The endpoint of this study is the number of cocaine use days during the 30 day evaluation period. Absent a treatment effect, it is assumed that each individual's daily use follows a Bernoulli distribution, but that individual's use risk varies, with sufficient population variability to match the anticipated extra-binomial variability noted from the prior study. Specifically a beta-binomial distribution is assumed for daily use with parameters (b1= .45, b2=1). Since the mean of the beta binomial is b1/b1+b2, then the expected number of use days in a 30 day period is 9.31 and the standard deviation is 9.08.

While verification of some daily reports will be substantiated with urine testing, underreporting of use may occur. We anticipate that this underreporting may vary among individuals. In the simulation underreporting of use is modeled under assumptions of complete accuracy (0% underreporting), 20% underreporting and 40% underreporting of use days. Conditional on use, the probability of underreporting is modeled with a beta-binomial distribution with parameters of (.2, .8) for the 20% level and (.4, .6) for the 40% level.

Losses to follow-up are assumed to occur in 5% of the participants prior to initiation of the evaluation period. In addition, a daily loss probability is presumed that is scaled by the individuals mean use probability from the initial beta-binomial distribution. Thus, individuals with higher use rates are more likely to discontinue. In the simulation, the unscaled daily probability is set at .008 and this results in an 18% dropout rate during the evaluation period.

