#### **10.4** Significance Testing

A 5% level test will be used for the analysis of the primary endpoint comprised of 2 pairwise 2.5% level one sided tests of the two buprenorphine arms versus the no-buprenorphine arm.

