#### **10.6** Exploratory Analyses

The primary endpoint will be analyzed with the 2 sample Wilcoxon statistic. If the opioid history strata is identified as a significant predictor of cocaine use days with a mean difference >3.0 days, then the primary endpoint will be analyzed with a stratified Wilcoxon test.

The effect in the "high" versus "low" opioid involvement strata is of interest; strata-specific assessment of the primary outcome will be evaluated.

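### Site is a randomization stratum but enters no version of the primary Wilcoxon test, so the test is mildly conservative and forgoes a little power if cocaine use differs materially between sites

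*Protocol*

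**What the plan says.** - **Allocation (Protocol 7.2, 5.5, 10.2.2).** "Randomization will be stratified according to site and opioid use levels according to the following strata". The schedule uses "balanced blocks of varying sizes within strata". On sites: "The multi-site trial will involve 10-12 community treatment programs across the CTN", with about 30 randomized at each.
- **Primary test (10.3, 10.4).** "The primary endpoint will be analyzed with the 2 sample Wilcoxon statistic". It is applied as "2 pairwise 2.5% level one sided tests of the two buprenorphine arms versus the no-buprenorphine arm".
- **Conditional stratified version (10.6).** The same test is restated, then replaced by a stratified Wilcoxon under one condition: "If the opioid history strata is identified as a significant predictor of cocaine use days with a mean difference >3.0 days". Site is not mentioned.
- **Supporting analyses (10.3).** "Additional analyses will examine the primary endpoint adjusting for strata and other covariate effects including gender, age and race". Whether the strata meant here include site is not stated.
- **Sample size (10.2).** "The study has been designed to include 300 individuals randomly assigned at a 1:1:1 ratio to the 3 treatment arms". The simulation behind the power table has no site term.

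**The concern.** Blocking within site makes the arms nearly equal in number at every program, so differences in cocaine use between programs largely cancel out of the arm comparison. The variance of the ordinary two-sample Wilcoxon assumes unrestricted allocation and still counts those differences as noise. If programs differ, the standard error is too large: the test rejects less often than 2.5% under the null and detects a real effect less often than it could. Part of the precision gained by stratifying on site is then left unused in the one test that carries the efficacy claim. Using a factor that the trial already randomizes by needs no extra data.

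**Working it through.** **1. Reproduce the plan's own figures.** Inputs from 10.2: daily use beta-binomial (.45, 1) over 30 days, 5% lost before the evaluation period, daily loss .008 scaled by individual use risk, dropouts scaled to 30 days, one-sided 2.5%.

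- Mean = 30 × .45/1.45 = 9.31.
- With p = .3103 and ρ = 1/2.45 = .408, SD = √[30 × p(1−p) × (1 + 29ρ)] = √(6.42 × 12.84) = 9.08. Both match 10.2.
- 10.2 does not say how treatment acts. Subtracting .10, .15 or .20 from each person's daily risk (floor at 0) gives 2.27, 3.18 and 3.99 days, close to the table's 2.27, 3.16 and 3.94.
- With 95 analysed per arm and no underreporting, simulated power is .62, .87 and .98, against .635, .886 and .974 in the table.

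**2. The two variances.** Rank everyone in a contrast together. Let N be the total, n and m the arm sizes, S² the variance of all the ranks, and subscript k denote site.

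- Unstratified: R − n(N+1)/2, with variance (nm/N)·S².
- Within site: Σ(R_k − n_k·r̄_k), with variance Σ(n_k·m_k/N_k)·S_k².

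With arms balanced in every site the two numerators are equal, and only the variances differ. The unstratified variance is larger by roughly 1/(1 − ICC), taking the ICC of the ranks as close to that of use days. The effective critical value is therefore about 1.96/√(1 − ICC).

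**3. Analytic size.** The site ICC is an assumption. Latent values of .05, .10 and .15 corresponded to about .04, .08 and .12 in control-arm use days, that is, a between-site SD of √ICC × 9.08 ≈ 1.8, 2.6 and 3.1 days.

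- .04: 1.96/√.96 = 2.00, one-sided error 2.3%
- .08: 1.96/√.92 = 2.04, one-sided error 2.1%
- .12: 1.96/√.88 = 2.09, one-sided error 1.8%

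**4. Simulation.** Model of step 1, 10 sites with 10 per arm each, site effect through a Gaussian copula on individual risk. Runs A (12,000 replications per cell) and B (18,000) balance arms exactly within site. Run C uses permuted blocks of 3 and 6 within site × opioid stratum (block sizes assumed). Each cell gives unstratified / pooled-rank site-stratified, in %.

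| Latent ICC | Power, 3.18 days: A | B | C | Power, 2.27 days: A | B |
|---|---|---|---|---|---|
| 0 | 89.6 / 89.5 | 89.0 / 88.9 | 89.3 / 89.2 | 63.7 / 63.8 | 63.4 / 63.4 |
| .05 | 89.6 / 90.3 | 89.6 / 90.3 | 89.6 / 90.2 | 64.4 / 65.4 | 64.0 / 65.4 |
| .10 | 90.0 / 91.3 | 90.1 / 91.4 | 89.6 / 90.7 | 64.1 / 67.0 | 64.3 / 67.2 |
| .15 | 90.5 / 92.2 | 90.9 / 92.7 | 90.5 / 92.3 | 64.9 / 68.9 | 65.4 / 69.7 |

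- In run C the gain at 2.27 days was also about 3 to 4 points at ICC .10 to .15.
- Unstratified one-sided error in run A was 2.5, 2.3, 2.2 and 1.7% at ICC 0, .05, .10 and .15. Run B gave 2.0% at .10 and 1.8% at .15; run C gave 1.8% at .15. The averages are 2.1% at .10 and about 1.8% at .15, in line with step 3. The stratified test stayed at 2.4 to 2.5%.
- With 12 sites × 8 per arm at 3.18 days, power was 88.3 / 88.0% at ICC 0 and 89.4 / 90.6% at ICC .10.

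**5. Van Elteren by site is not equivalent.** It ranks within small sites. At ICC 0 and 3.18 days its power was 88.1% against 89.6% unstratified in the run A design. With a logit-scale site effect and blocked allocation it was .870 against .887. In that second model it only broke even at a use-day ICC of about .04 (.883 against .882).

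**The case against.** The strongest defence is that a simple rank test, valid and at worst slightly conservative, is a legitimate choice. Much of it stands.

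- **Validity.** The 2.5% level holds as an upper bound.
- **Stated power.** Unstratified power does not fall as the ICC rises in the table above. With the logit-scale site effect it stays above the protocol's 85% up to a use-day ICC of .26 (.871). What is lost is an available gain.
- **Small site differences.** With blocks of 3 and 6 and 6,000 replications, unstratified against stratified power was 88.8 against 89.2% at latent ICC .03 and 89.8 against 90.4% at .05, with unstratified error at 2.5% in both. With unequal sites (8 to 70, assumed) it was 89.1 against 89.3% and 90.1 against 90.5%.
- **No ICC in the document.** Nothing in the protocol shows that site differences reach the range where the gain is visible.

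Two further arguments stand only in part. The stratum-adjusted analysis in 10.3 is planned, so one cannot say that no analysis could take account of site. But it is additional, does not carry the error rate in 10.4, and leaves site unstated. A reference distribution could also be set in a statistical analysis plan. But 10.3 fixes the two-sample Wilcoxon, 10.6 repeats it, and where the protocol stratifies that test it names opioid history only.

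A reader might infer that the test falls below its level and wastes power whenever sites differ at all, or that the power table is overstated. The figures support neither.

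**Conclusion.** The mismatch is real and its consequence is modest. Site is balanced by design and ignored in the primary test. At an assumed latent ICC of .10 to .15, one-sided error is about 1.8 to 2.1% instead of 2.5%. The test then forgoes 1.1 to 1.8 points of power at 3.18 days and 2.9 to 4.3 points at 2.27 days, where the plan's own power is only .635. At .05 the loss is 0.6 to 0.7 points at 3.18 days and 1.0 to 1.4 at 2.27 days; with no site differences there is none. This is a point of efficiency and calibration and does not threaten validity.

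The figures rest on the assumed ICC, the inferred form of the treatment effect, no underreporting, near-equal site sizes except where noted, and stratification by site alone. The site × opioid-level version of the test was not simulated.

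**What to change.** In 10.3, name one primary test, applied unconditionally to each buprenorphine-versus-placebo contrast: the Wilcoxon rank-sum on pooled ranks, referred to its permutation mean and variance within randomization strata. State now whether the strata are site or site × opioid level. Do not offer van Elteren by site as an equal option, because it loses about 1 to 2 points if sites do not differ.

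Reconcile 10.6 by removing the conditional switch of the primary test, so that only one definition remains; the stratum-specific assessments there can stay. Keep the unstratified Wilcoxon as a sensitivity analysis. In 10.3, say that the strata adjusted for in the additional analyses include site.

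The cost is a few sentences and no new data. If sites turn out alike, the largest simulated loss with the pooled-rank form was 0.3 points (12 sites), and about 0.1 with 10 sites.

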# 8.3 Drug Use Measures and Psychological Measures

# 8.3.1 Timeline Follow-back (TLFB)

The Timeline Follow-back procedure (Sobell & Sobell, 1992; Fals-Stewart, 2000) will be used to elicit the participant's self-reported use of alcohol and illicit substances before and during the entire study period. At screening, this form will be used to assess substance use reported by the participant for the 30-day period prior to screening. The TLFB will be administered at each study visit throughout the active treatment phase and through the end of the follow up period to document the participant's self-reported use of substances for each day since the previous TLFB assessment.

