#### **10.1.2** Primary Endpoint

The primary endpoint is the number of cocaine use days during the 30-day evaluation period. The evaluation period will be the last 30 days of the active medication period and will end on the day prior to initiation of the taper. Under the protocol schedule this would be days 25 to 54 inclusive. Cocaine use will be measured by self-report, corroborated with thrice-weekly urine drug screens. Scores for individuals who initiate the evaluation period will be included, and those who discontinue participation will have their score at the time of withdrawal scaled to the 30-day evaluation period.

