#### **10.7** Missing Data and Dropouts

The primary analysis will be performed in the group of individuals who initiate the evaluation period. Minimal loss is anticipated between randomization and this time point given the short time period. Intent-to-treat analysis with all cases will be performed assuming both the maximally pessimistic situation (all treated use daily, all control use never) and baseline use levels for these early withdrawals. The primary endpoint score imputes dropouts during the evaluation period to have use rates equal to that observed through the period prior to dropout. The TES will be used as a secondary analysis to assist with evaluating this effect. Note that in the design simulations, the TES 12-day analysis was observed to be less powerful than the analysis of the selected primary endpoint. But design assumptions did not assume interactions with treatment for either underreporting or withdrawal events.

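### The primary Wilcoxon test makes no use of the baseline 30-day cocaine use count already collected at screening: a valid test, but less efficient than it could be

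*Protocol*

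**What the plan says.** Protocol section 10.3 sets the primary test: "The primary endpoint will be analyzed with the 2 sample Wilcoxon statistic". Section 10.6 repeats it and allows one modification, a stratified Wilcoxon, under this condition: "If the opioid history strata is identified as a significant predictor of cocaine use days with a mean difference >3.0 days". The strata in section 7.2 are site and opioid use level; cocaine use is not a stratification factor.

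On adjusted analyses, section 10.3 says: "Additional analyses will examine the primary endpoint adjusting for strata and other covariate effects including gender, age and race".

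On the data available, section 8.3.1 says of the TLFB: "At screening, this form will be used to assess substance use reported by the participant for the 30-day period prior to screening". For the treatment period it says: "The TLFB will be administered at each study visit throughout the active treatment phase". Section 10.1.2 defines the endpoint measurement: "Cocaine use will be measured by self-report, corroborated with thrice-weekly urine drug screens".

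The one stated analytic use of pre-treatment cocaine use is in section 10.7. There an intent-to-treat sensitivity analysis assigns "baseline use levels for these early withdrawals".

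**The concern.** Section 10.2 describes an outcome dominated by differences between people: the assumed standard deviation (9.08 days) is nearly as large as the mean (9.31 days). A person's own count of use days before treatment is a natural predictor of that person's later count. If it is even moderately predictive, a test that ignores it leaves explainable variation in the noise.

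What is at stake is power. The protocol's table leaves little room in places: .777 at 3.16 days with 40% underreporting, and .515 to .635 at 2.27 days. The protocol already accepts that a prognostic variable can justify changing the primary test, but applies this only to opioid history and only after seeing the data.

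**Working it through.** **Inputs from the protocol (sections 10.2 and 10.4).** 100 randomized per arm, 5% lost before the evaluation period, so 100 × 0.95 = 95 per arm analysed. Daily use is beta-binomial with parameters .45 and 1. Daily dropout is .008 scaled by the person's use probability, with dropouts' scores scaled to 30 days. Each contrast is tested one-sided at 2.5%.

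**Check of the outcome model.** Mean = 30 × .45/1.45 = 9.31. Variance = 30 × .3103 × .6897 × (1 + 29/2.45) = 82.4, so SD = 9.08. Both agree with the protocol.

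**Reproducing the power table.** The protocol does not say how the effect was imposed. Of five mechanisms tried, subtracting a constant from each person's daily use probability, floored at zero, matches the table. Constants of 0.10 / 0.15 / 0.20 give effects of 2.27 / 3.18 / 3.99 days (protocol: 2.27 / 3.16 / 3.94). With 4,000 replications per cell and no underreporting:

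| Effect (days, protocol) | Protocol Wilcoxon | Reproduced Wilcoxon | Reproduced t-test |
|---|---|---|---|
| 2.27 | .635 | .644 | .418 |
| 3.16 | .886 | .890 | .703 |
| 3.94 | .974 | .980 | .893 |

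The t-test shortfall at the two smaller effects (about 23 and 19 points) agrees with the protocol's remark of roughly 20 points. With the underreporting columns included, seven of nine cells agree within 2 points. The other two, both at 3.16 days, are .848 against .873 and .754 against .777, about two standard errors of the protocol's 1,000 replications.

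**Adding the baseline.** The baseline count was given the same marginal distribution as the endpoint and linked to on-study use by a Gaussian copula. The test was Quade's rank analysis of covariance:
- Pool the two arms, rank the endpoint (R_Y) and the baseline count (R_B), and centre both.
- Slope b = Σ R_Y R_B / Σ R_B².
- Residual e = R_Y − b R_B.
- Compare residuals between arms one-sided at 2.5%.

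The correlation is **assumed**; the protocol gives none. Results with 95 per arm and no underreporting, against an unadjusted Wilcoxon at about .89 (3.16 days) and .63 (2.27 days):

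| Control-arm Spearman | Rank ANCOVA, 3.16 days | Rank ANCOVA, 2.27 days |
|---|---|---|
| 0 | .89 | .61 |
| 0.35 | .93 | .67 |
| 0.44 | .94 | .72 |
| 0.53 | .97 | .78 |
| 0.62 | .98 | .83 |

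Type I error was .019 to .029. A separate simulation of 3,000 replications per cell covers the low end and agrees closely elsewhere (Wilcoxon to rank ANCOVA):
- Correlation 0: .894 to .892 at 3.16 days, .631 to .632 at 2.27 days.
- Correlation 0.16: .893 to .900 and .638 to .647.
- Correlation 0.34: .886 to .921 and .636 to .688.
- Correlation 0.63: .888 to .981 and .631 to .835.

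The .61 at zero correlation is therefore best read as simulation noise: nothing material is lost when the baseline is uninformative.

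**The case against.** The strongest defence is that nothing here is wrong. The Wilcoxon controls its error rate, was chosen by simulation over a t-test and a repeated-measures model, and reaches its design target. That stands, and it limits the point to efficiency. The simulation comparison does not settle the matter, though, because neither rejected alternative is said to include baseline use.

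A second defence is that the adjusted analyses list covariates as examples, so baseline use could still be added to the supportive models in a later analysis plan. That also stands. A reader might infer that the protocol rules baseline cocaine use out of every analysis; the open wording of section 10.3 does not support that. The primary test is different. Sections 10.3 and 10.6 name it outright, and section 12.7 says the analysis will follow the protocol's own analytical section.

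Third, the correlation may be weak. Up to 30 days of screening, opioid detoxification, naltrexone induction, CBT and 24 days of treatment lie between the two windows. The baseline is a single 30-day recall, whereas the endpoint is recalled visit by visit and backed by thrice-weekly urine screens. The shared element is the self-report instrument, not the whole measurement. This stands as a reason to show the gain as a range that includes zero.

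A reader might infer from the stable individual use risk in section 10.2 that baseline and endpoint would correlate almost perfectly, and so that the loss is very large. The documents do not support this. The model is specified for the 30-day evaluation period and says nothing about behaviour before screening.

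A reader might also infer that chance baseline imbalance makes the unadjusted result unsound. It does not: randomization places such imbalance within the test's Type I error, and section 10.8 provides for describing baseline by arm.

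**Conclusion.** The point holds as an avoidable loss of efficiency in a primary test that the protocol fixes as unadjusted. It is not an invalid test or a failure to meet the stated power. At the 3.16-day design effect the gain is negligible at correlations of 0.16 or less, about 4 to 5 points at 0.35 to 0.44, and 8 to 9 points at 0.53 to 0.62. At 2.27 days the gains at 0.35 / 0.44 / 0.53 / 0.62 are about 4 / 9 / 15 / 20 points.

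These sizes rest on the assumed correlation, the copula link, the subtractive effect that reproduces the protocol's table, and no underreporting. The direction holds for any appreciable correlation.

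**What to change.** In sections 10.3 and 10.4, pre-specify as the primary test for each contrast a Quade rank analysis of covariance of cocaine use days in the evaluation period on baseline TLFB cocaine use days, at the same one-sided 2.5% level. Keep the unadjusted Wilcoxon as a sensitivity analysis. Name baseline cocaine use days among the covariates for the adjusted analyses in section 10.3. Bring section 10.6 into line, since it restates the Wilcoxon and its conditional stratified version.

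No new data are needed and the approach stays rank-based. The small cost is re-running the power table in section 10.2 and rechecking the futility description in section 10.5, including its figure of about 20% conditional power, under the new test. The power section should state the baseline/endpoint correlation it assumes and show results for a range that includes low values.

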#### 6.2 Secondary Outcome Measures

- 1. Adverse events related to study medication across the duration of the study, measured at each clinic visit by appropriately qualified and trained medical personnel;
- 2. Cocaine use will be assessed by a number of outcome measures, including:
  - a. The Treatment Effectiveness Score using urine drug screen results;
  - b. Number of cocaine use days as measured by self-report during the period between randomization and end of treatment;
  - c. Percentage of participants who test free from cocaine use on three successive urine tests;
- 3. Number of days of use of other drugs of abuse as measured by self-report, corroborated by urine drug screen results;
- 4. Severity of cocaine and opioid craving using Visual Analog Craving Scales (VAS);
- 5. Change in depressive symptoms during the period between randomization and end of treatment as measured by the BDI.
- 6. Reduction in drug-related problems between randomization and end of treatment as indicated on the Addiction Severity Index;
- 7. Changes in quality of life between randomization and end of treatment as measured by the World Health Organization Quality of Life BREF instrument;
- 8. Percentage of participants who achieve cocaine abstinence throughout the final two weeks of the evaluation period.
- 9. Percentage of participants who are retained in treatment for the duration of the active treatment phase.
- 10. Number of cocaine use days as measured by self-report during the follow-up period.

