# 8.3.6 World Health Organization Quality of Life BREF (WHOQOL-BREF)

The WHOQOL-BREF (The WHOQOL Group, 2004) instrument comprises 26 items, which measure domains of physical health, psychological health, social relationships, and environment. The WHOQOL-BREF is a shortened version of the original instrument that may be more convenient for use in large research studies or clinical trials. It assesses the individual's perceptions in the context of their culture and value systems, and their personal goals, standards and concerns. The WHOQOL instruments were developed collaboratively in a number of centers worldwide, and have been widely field-tested. The WHOQOL-BREF will be self-administered at screening, at the end-of-medication visit (if medication is stopped early), at the end-of-treatment visit (last visit of Week 8), and at the 3-month follow up.

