#### 8.3.12 Addiction Severity Index Lite (ASI-Lite)

The ASI-Lite is derived from the Fifth Edition of the ASI (McLellan et al., 1992), a structured clinical interview that yields scores for seven areas of functioning typically impacted by addiction, including medical status, employment status, drug use, alcohol use, family status, legal status, and psychiatric status. The ASI-Lite will be completed at screening, at the end-of-medication visit (if medication is stopped early), at the end-of-treatment visit (last visit of Week 8), and at each follow-up.

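### Change in WHOQOL-BREF and ASI scores is compared by a valid but unadjusted Wilcoxon test; conditioning on the screening score would usually be more precise

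*Protocol*

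**What the plan says.** Protocol section 6.2 defines secondary outcome 6 as "Reduction in drug-related problems between randomization and end of treatment as indicated on the Addiction Severity Index". Secondary outcome 7 is worded the same way: "Changes in quality of life between randomization and end of treatment", measured by the WHOQOL-BREF.

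Section 10.3 fixes the analysis. The quantity analysed is change: "Changes occurring over the treatment period in severity and type of drugrelated problems and in quality of life will be summarized". For scores on a continuous scale, the plan is that these changes are "compared between treatment groups using the two sample Wilcoxon test for continuous outcomes"; categorical items get a chi-square or Fisher's exact test instead.

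Both baselines exist. Section 8.3.6: "The WHOQOL-BREF will be self-administered at screening". Section 8.3.12: "The ASI-Lite will be completed at screening". Table 2 shows no later pre-randomization measurement of either instrument, so the screening score is the baseline.

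Elsewhere in section 10.3, covariate adjustment is described for the primary endpoint only: "Additional analyses will examine the primary endpoint adjusting for strata and other covariate effects including gender, age and race". The longitudinal models name other outcomes: "Repeated-measurement analysis models will be used to explore presence of time-related treatment effects, including severity of cravings and level of mood disturbance". Neither sentence names the ASI or the WHOQOL-BREF, or an outcome's own baseline as a covariate.

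**The concern.** A change score gives the baseline a fixed weight of one, whatever the correlation between the two measurements. When that correlation is below one, participants with poor screening scores improve on average without any treatment effect, and this predictable part of the change stays in the comparison as noise. Any chance difference between arms at screening also moves the observed difference in change. Regressing the end score on the screening score lets the data choose the weight and removes that noise.

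At stake is precision on secondary objectives 6 and 7. Section 10.5 gives the need for precise estimation of several outcomes as one reason for not stopping early for efficacy, so a less precise method for two named outcomes sits awkwardly with the protocol's own aim. Section 10.8 allows informal comparison of baselines, or a test if differences are suspected, but provides no adjustment to follow.

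**Working it through.** **Inputs from the protocol.** 300 randomized 1:1:1, so 100 per arm (section 10.2). Loss of 5% before the evaluation period (section 10.2), used here only to illustrate 95 per arm. Strata are site by two opioid-use levels (section 7.2), with 10 to 12 sites (section 5.5). The protocol gives no effect size, SD, correlation, power or significance level for these two outcomes, so there is no stated figure to reproduce.

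**Assumed inputs.** Equal variance s² at screening and end of treatment; a linear relation with correlation rho, shown over a range; two-sided 5%.

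**Variance.** Per participant:

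- Change: Var = 2(1−rho)s².
- End score given screening score: Var = (1−rho²)s².
- Ratio, adjusted to change: (1−rho)(1+rho) / [2(1−rho)] = (1+rho)/2.
- The excess in the change score is 2(1−rho) − (1−rho²) = (1−rho)², in units of s². This is the regression-to-the-mean part.

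**Power, normal approximation.** If the comparison of change has 80% power, the adjusted comparison has power Φ[(1.96 + 0.84)/√ratio − 1.96].

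| rho | Var change | Var adjusted | Excess | Ratio | Power (change = .80) |
|---|---|---|---|---|---|
| .3 | 1.40 | .91 | .49 | .65 | about .93 |
| .5 | 1.00 | .75 | .25 | .75 | .90 |
| .7 | .60 | .51 | .09 | .85 | .86 |
| .9 | .20 | .19 | .01 | .95 | .82 |

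So 100 per arm on plain change is worth about 65, 75, 85 or 95 per arm with adjustment.

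**Simulation of the planned test.** 95 per arm, 1,500 replicates, effect set so that a t-type comparison of normal change scores has 80% power. Rank ANCOVA regresses the rank of the end score on arm and the rank of the screening score. The skewed case uses lognormal scores (log SD 0.8, rescaled to unit SD, additive effect), with rho on the log scale.

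| Scores | rho | Wilcoxon on change | Linear ANCOVA | Rank ANCOVA |
|---|---|---|---|---|
| Normal | .3 | .77 | .93 | .92 |
| Normal | .5 | .78 | .90 | .88 |
| Normal | .7 | .77 | .85 | .81 |
| Skewed | .3 | .98 | .92 | 1.00 |
| Skewed | .5 | .98 | .87 | 1.00 |
| Skewed | .7 | .98 | .80 | 1.00 |

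A run with 90 per arm and normal scores agreed: Wilcoxon .77/.76/.77, linear ANCOVA .93/.90/.85, rank ANCOVA .91/.88/.82. With normal scores both adjusted methods gain. With these skewed scores linear ANCOVA loses to the planned test, while rank ANCOVA does at least as well in every case simulated.

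**Cost of stratum terms.** Site by opioid level gives 10×2 = 20 to 12×2 = 24 cells. At 2×95 = 190 participants per contrast, that is 190/24 = 7.9 to 190/20 = 9.5 per cell, and 19 to 23 parameters. A full set of cells would take back part of the gain. The simulations include no stratum terms, so they do not measure this cost.

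**The case against.** The strongest case against is that nothing here is wrong. A two-sample Wilcoxon test on change holds its error rate under randomization, these are supportive outcomes with no power claim, and a statistical analysis plan could add an adjusted analysis. The first two parts stand, and they make this a minor point. The third stands only in part. Section 10.3 does not leave the method open but names the test, and section 12.7 says the analysis will follow the protocol's analytical section. Nothing in either forbids an added analysis.

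Three stronger readings are tempting, and the protocol does not support them.

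- A reader might infer that the screening scores are ignored. They are not: sections 6.2 and 10.3 compare change, so the baseline is subtracted from every end score. What is missing is conditioning on it.
- A reader might infer bias from regression to the mean or chance imbalance. Regression to the mean acts alike in all randomized arms, and chance imbalance is already covered by the test's error rate. Both add variance; neither biases the comparison.
- A reader might take the simulated gains as the loss in this trial. They rest on an assumed correlation, effect size and score distribution. The gain nearly vanishes at rho .9, and with skewed scores linear ANCOVA can do worse than the planned test. Recommending ANCOVA without regard to shape would therefore be a mistake.

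**Conclusion.** The point holds as a modest gain in efficiency. The planned comparison is valid but does not condition on a screening score that the trial already collects. Under equal variances and a linear relation, the adjusted comparison has .65 to .85 of the variance for an assumed rho of .3 to .7, and .95 at rho .9. The actual loss cannot be sized from the protocol. A rank-based adjustment is the safer default, because it was no worse than the planned test for both the normal and the skewed scores simulated. The point concerns only the continuous WHOQOL-BREF and ASI scores.

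**What to change.** In section 10.3, or in the statistical analysis plan before unblinding:

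- Compare end-of-treatment WHOQOL-BREF domain and ASI composite scores between each buprenorphine arm and control with the screening score as covariate. Use rank ANCOVA by default, and linear ANCOVA only where scores are roughly symmetric.
- Include the opioid-use stratum. Handle site parsimoniously, for example as a random effect or with small sites pooled, not as 20 to 24 site-by-stratum cells.
- Report an adjusted difference with a 95% CI. A rank model gives no difference on the score scale, so say where the estimate comes from (for example a linear model with a bootstrap interval) and that the rank test carries the inference.
- Keep the Wilcoxon test on change as a sensitivity analysis.

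Section 6.2 can stay as written: in a linear model containing the screening score, the treatment coefficient is the same for the end score and for change. The cost is a few sentences of wording, with no new data, visits or participant burden. Fixing it before unblinding keeps the choice from looking driven by results.
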